## 8.2 Primary Statistical Objective

The primary statistical objective is to evaluate the efficacy of the device by estimating the change from baseline in the 12 month IPSS within +/- 1 unit.

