## 8.3 Sample Size

The sample size is based on the following assumptions

- Four countries with asymmetrical countrywide enrollments ranging from 15% to 25% of the total enrollment (conservative assumption)
- Standard Deviation = 8.5
- Difference between the lower and upper 2-sided 95% Confidence interval = 2
- 10% of patients missing either baseline or 12 month IPSS

A sample size of up to 500 patients is required to estimate the 12 month change from baseline in the IPSS within +/- 1 unit. Sample size calculations were performed using NCSS PASS 2020's procedure for one mean in a stratified design.

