### 8.5.2.1 Missing Data

Missing data for the IPSS will be imputed as the age-specific average for that time point. Also, a tipping point analysis will be performed where the analysis will be performed, excluding the missing data. The number of missing data points it takes to tip the results from one direction to the other will be reported.

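### The tipping point analysis of 12-month IPSS has no assigned values and no threshold, and no planned analysis lets missing men do worse than comparable observed men

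*Combined protocol and SAP*

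**What the plan says.** Section 8.5.2.1 fills in a missing IPSS with the mean for the man's age group at that visit. It then states that "a tipping point analysis will be performed where the analysis will be performed, excluding the missing data", and that "The number of missing data points it takes to tip the results from one direction to the other will be reported". It does not say what values missing men would take, what shift would be applied, or what counts as a direction.

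Section 8.2 sets the primary objective as "estimating the change from baseline in the 12 month IPSS within +/- 1 unit". Section 8.5.2 delivers a country-stratified mean with a 95% confidence interval and names no null value, performance goal or comparator. Section 8.5.1.3 sets a default two-sided 0.05 level but attaches no hypothesis to this endpoint.

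Two other sections matter. Section 8.5.3.1 models IPSS over time with a mixed model on unimputed data, and adds complete-case and age-average sensitivity runs. Section 7 discontinues a man who has a non-PAE BPH procedure (other than biopsy) after his study PAE and stops collecting his follow-up data.

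**The concern.** A tipping-point analysis gives missing patients progressively worse outcomes until a stated conclusion changes. It needs a rule for the assigned values and a conclusion that can change. Section 8.5.2.1 supplies neither. Once the missing men are excluded, the promised count cannot be computed, and two programmers would not arrive at the same number.

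What is at stake is the meaning of the robustness statement in the final report. Men who go on to another BPH procedure before month 12 have plausibly responded poorly, and they will have no 12-month score. Age-mean imputation gives them the average of observed men, and the complete-case run drops them. Both treat missing men as resembling observed men, so the two results will tend to agree whether or not that is true. A sign-based count would add further reassurance without testing the point.

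**Working it through.** **Inputs**

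- Precision target: half-width 1, from "Difference between the lower and upper 2-sided 95% Confidence interval = 2" (Section 8.3).
- "Standard Deviation = 8.5" and "10% of patients missing either baseline or 12 month IPSS" (Section 8.3).
- Background mean IPSS: 21.5 at baseline and 6.2 at 9 to 16 months (Section 1), so a change of 6.2 - 21.5 = -15.3. This is an illustration. The plan makes no assumption about the size of the effect.

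**The plan's own figure.** For one mean, n = (1.96 × 8.5 / 1)² = 277.6, so 278 evaluable and 278 / 0.9 = 309 enrolled. This does not reproduce 500, but the plan says up to 500 and does not give the full stratified inputs. With 500 enrolled and 450 evaluable, the half-width is 1.96 × 8.5 / √450 = 0.785, inside the target. Nothing below depends on this difference.

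**Formulae.** Let p be the missing share, d_obs the mean change in observed men and d_mis that in missing men.

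- Overall mean = (1 - p) × d_obs + p × d_mis.
- Shift from the observed-men estimate = p × (d_mis - d_obs). If the gap is the same in every country, weighting countries by enrolment gives the same result.

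**Reading 1: tipping means a change of sign**

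- Setting the overall mean to zero gives d_mis = -d_obs × (1 - p) / p.
- At p = 0.10 this is 15.3 × 0.9 / 0.1 = 137.7 points of worsening, about 6.4 times the baseline mean of 21.5.
- If the 95% CI need only reach zero (500 enrolled, assigned values treated as fixed), it is 0.9 × (15.3 - 0.785) / 0.1 = 130.6 points.
- If every missing man had no change, the overall mean would be -15.3 × (1 - p), which is negative for any share short of 100%.
- The result does not depend heavily on -15.3: at 10% missing, the required worsening is always nine times the observed improvement.

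**Reading 2: how far can the estimate move?** All of the 10% are treated as lacking the 12-month score. The plan's 10% also includes men missing only the baseline score.

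| Missing men, p = 0.10 | Gap from observed men | Shift in estimate |
|---|---|---|
| Gap that gives a 1-unit shift | 1 / 0.10 = 10 | 1.0 |
| Half the observed improvement (-7.65) | 7.65 | 0.77 |
| No change (0) | 15.3 | 1.53 |

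As counts out of 500, a 1-unit shift needs 1 / 15.3 = 6.5%, or 33 men, if missing men had no change. It needs 1 / 7.65 = 13.1%, or 66 men, if they improved half as much. Counts of this kind are informative because the assigned value and the threshold are both stated.

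**The case against.** Much of the case on the other side stands.

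- The plan promises a count, so its authors intended more than a complete-case run. The fair criticism is that the analysis is named without being specified.
- A reader might infer that this is the only sensitivity analysis bearing on 12-month IPSS. It is not. The mixed model in Section 8.5.3.1 uses the 3-month score and does not impute, so it can allow for a man already doing poorly at 3 months. But it still assumes that a missing man resembles observed men with a similar history, and its two sensitivity runs do not relax that.
- A reader might infer that ordinary missingness will push the estimate outside 1 unit. The documents do not show this. At 10% missing the gap must exceed 10 points, and missing men with half the observed improvement leave the shift at about 0.8.
- The 1-unit figure is a confidence-interval half-width, a target for sampling precision and not a stated tolerance for bias. I use it because it is the only margin the plan offers.
- A reader might raise the missing share by adding men with indwelling catheters (54 of 286, or 18.9%, in the background cohort). Section 3.1 limits the primary objective to men eligible to complete a baseline IPSS, Section 4 does not require the IPSS of catheterised men, and Section 8.4.2 removes men with a catheter at the end of the procedure from the evaluable set. They lie largely outside the target population and should not be counted as missing from it.
- A reader might take the 3-point reduction in Section 1 as a tipping threshold. It is a per-patient criterion there. It could not tip either: with no change in the missing 10%, the mean is still 0.9 × -15.3 = -13.8.

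**Conclusion.** The point holds in this limited form. Followed as written, Section 8.5.2.1 yields either a complete-case estimate or a count that cannot be computed without further choices. If that count is read as a change of sign, it says nothing useful about an estimate meant to be good to 1 unit: about 138 points of mean worsening would be needed at 10% missing.

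The unexamined risk is moderate. It amounts to about 0.8 units if missing men improved half as much as observed men and about 1.5 if they did not improve at all. These two sizes rest on the background change of -15.3 and on the plan's 10% missing. The 10-point gap for a 1-unit shift rests on the 10% alone. The documents do not say how many men will have another procedure before month 12, so neither the likelihood nor the actual size of a bias can be stated. The conclusion is that the plan has no means of showing it. The primary estimate itself is not shown to be wrong.

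**What to change.** In Section 8.5.2.1:

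1. Call the run that excludes missing data a complete-case analysis.
2. Replace the tipping count with multiple imputation of missing 12-month IPSS, using baseline and 3-month IPSS, age and country. Add a delta to the imputed 12-month scores in 1-point steps, from zero up to no change from baseline.
3. Report the mean change and 95% CI at each delta, and the delta at which the estimate moves by more than 1 unit from its value at delta zero. At 10% missing that crossing should come at about 10 points.
4. Report the number of men with an imputed 12-month score, separating those discontinued after a non-PAE procedure from the rest, so that the reader can judge which deltas are credible.

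The cost is SAP wording and a modest programming step, with no new data collection and no change to sample size. Another clearly specified method would also serve, provided it states the values assigned to missing men and the criterion for judging the result.

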### 8.5.2.2 Multivariate Model

A multivariate linear model will be developed to describe the IPSS changes over time. Univariate analysis will be performed analyses for all the baseline characteristics. Based on those results combined with clinical judgment, a final set of baseline characteristics will be created for use in the multivariate model. LASSO (least absolute shrinkage and selection operator; also Lasso or LASSO) regression analysis method will be used to perform variable selection and regularization to minimize the unexplained variability and enhance the interpretability of the statistical model it produces.

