### **3.3 Exploratory Objectives:**

If sufficient data is available, additional exploratory analyses will also be conducted. These may include, but are not limited to:

- Comparison of safety and effectiveness outcomes from patients treated with Embosphere Microspheres 100-300 $\mu$  vs 300-500 $\mu$
- Comparison of procedure time for patients embolized with radial vs femoral access
- Comparison of safety and effectiveness outcomes of embolizations that were/were not performed using the PErFecTED technique
- Comparison of effectiveness outcomes of bilateral vs unilateral embolizations
- Multivariate analyses to determine factors correlated to better effectiveness outcomes
- Evaluation of change from baseline prostate size at any time point post PAE

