## 6 Visit schedule and actions

### 6.1 Baseline Visit

The following baseline data will be collected:

- Date patient signs informed consent
- Demographics
- Prior BPH procedures
- Current Medication for BPH (5 $\alpha$ -Reductase inhibitors,  $\alpha$ -blockers, ED medications, OTC medications, etc.)

The following baseline data will be collected within 4 weeks of the study PAE procedure:

- International Prostate Symptom Score (IPSS)
  - Must be self-administered by patient
- Sexual Health Inventory for Men (SHIM)
  - Must be self-administered by patient

The following baseline data will be collected within a timeframe consistent with standard of care:

- Prostate Size Assessment
- Urinary Evaluations (Indwelling urinary catheter use, Maximum urine flow rate (Qmax), and Post void residual volume (PVR)), if done
- Prostate specific antigen (PSA), if done

The following baseline data will be collected within 12 months of the study PAE procedure:

- Prostate Biopsy, if done

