## 8.5.2 Analysis of the Primary Endpoint

The stratified sample mean change from baseline in 12 month IPSS is estimated as follows.

$$\bar{x} = \sum_{h=1}^L \frac{N_h}{N} \sum_{i=1}^{n_h} \frac{X_{hi}}{n_h} = \sum_{h=1}^L \frac{N_h}{N} \bar{x}_h$$

where  $\bar{x}$  is the stratified sample mean,  $L$  is the number of strata,  $X_{hi}$  is change from baseline in 12 month IPSS for the  $i^{th}$  patient in the  $h^{th}$  stratum,  $N$  is the overall sample size and  $N_h$  is the sample size in stratum  $h$

It can be shown in T. Yahane(1967) that the expected value and variance of  $\bar{x}$  ( $V(\bar{x})$ ) assuming sampling without replacement are

$$E(\bar{x}) = \mu$$

$$V(\bar{x}) = \sum_{h=1}^L \left(\frac{N_h}{N}\right)^2 \left(\frac{N_h - n_h}{N_h n_h}\right) S_h^2$$

$$S_h^2 = \frac{1}{N_h - 1} \sum_{i=1}^{N_h} (X_{hi} - \mu_h)^2$$

where

The 95% confidence interval ( $CI(\mu)$ )s calculated as follows:

$$CI(\mu) = \bar{x} \pm z_{1-\alpha/2} \sqrt{\hat{V}(\bar{x})}$$

where  $\alpha$  is the type I error and  $\hat{V}(\bar{x})$  is the unbiased estimator of  $V(\bar{x})$  and is calculated as follows:

$$\hat{V}(\bar{x}) = \sum_{h=1}^L \left(\frac{N_h}{N}\right)^2 \left(\frac{N_h - n_h}{N_h n_h}\right) S_h^2$$

$$s_h^2 = \frac{1}{n_h - 1} \sum_{i=1}^{n_h} (X_{hi} - \bar{x}_h)^2$$

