## 8.5.3 Analysis of the Secondary Endpoints

### 8.5.3.1 IPSS changes over time

The changes over time in the IPSS using the EAS will be modeled using a linear mixed model where country and patient will be considered a random effect. If there is evidence of non-linearity, a nonlinear mixed-effects model using a 3rd-degree

 Tibshirani, Robert (1996). "Regression Shrinkage and Selection via the lasso". Journal of the Royal Statistical Society. Series B (methodological). Wiley. 58 (1): 267–88. JSTOR 2346178.

polynomial will be implemented. The predicted curve and 95% confidence interval will be reported. Missing data will not be imputed.

Sensitivity analyses using complete cases and missing values replaced with an age-specific average will be performed.

A multivariate linear model will be developed to predict the IPSS changes over time. Univariate analysis will be performed analyses for all the baseline characteristics. Based on those results combined with clinical judgment, a final set of baseline characteristics will be created for use in the multivariate model. The LASSO regression analysis method will be used to perform variable selection and regularization.

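### If the predictor models take IPSS change from baseline as response, an unadjusted screen followed by LASSO lets mathematical coupling with baseline IPSS influence which factors are selected

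*Combined protocol and SAP*

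**What the plan says.** Two sections of the combined protocol and SAP describe nearly the same model-building exercise.

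- Section 8.5.2.2, under the primary analysis: "A multivariate linear model will be developed to describe the IPSS changes over time".
- Section 8.5.3.1, under the secondary analyses: "A multivariate linear model will be developed to predict the IPSS changes over time".

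Both begin with a one-at-a-time screen: "Univariate analysis will be performed analyses for all the baseline characteristics". Then: "Based on those results combined with clinical judgment, a final set of baseline characteristics will be created for use in the multivariate model". LASSO does the variable selection and regularisation.

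IPSS is among the baseline data. Section 6.1 lists it, with SHIM, under "The following baseline data will be collected within 4 weeks of the study PAE procedure". No candidate list is given. Nothing removes baseline IPSS from the candidates, adjusts the screen for it, or protects it from the LASSO penalty.

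The model response is not defined. Section 8.5.2 does define the variable for the primary estimate, which "is change from baseline in 12 month IPSS for the" individual patient. Section 3.3 gives the purpose of such models: "Multivariate analyses to determine factors correlated to better effectiveness outcomes".

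**The concern.** Change is follow-up minus baseline. If change is the response and baseline IPSS is a candidate, the same measurement, with its error and its day-to-day fluctuation, stands on both sides of the equation. A negative association between baseline and change then appears even when the baseline score says nothing about where the patient ends up.

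Two consequences follow. First, a strong baseline coefficient is easily read as showing that men with worse symptoms gain more from PAE. The study has a single arm (Section 4), so no control group can separate regression to the mean from treatment effect. Second, the screen is unadjusted, so any characteristic correlated with baseline IPSS picks up part of the coupling and may be carried forward for that reason alone. Both bear on the Section 3.3 question of which factors go with better outcome.

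**Working it through.** The plan gives no figure for the predictor models, so there is none to reproduce. The check asks how large the coupling would be on figures found in the document.

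**Inputs**
- Baseline IPSS SD: 6.8 (Section 1, earlier 286-patient cohort).
- Follow-up IPSS SD: 5.8 (same cohort, 9–16 months).
- "Standard Deviation = 8.5" (Section 8.3), read here as the SD of the 12-month change. The section does not label it, but the sample size is for that change.

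**Step 1: implied baseline/follow-up correlation**
- cov(B,F) = (6.8² + 5.8² − 8.5²)/2 = (46.24 + 33.64 − 72.25)/2 = 3.815.
- r = 3.815/(6.8 × 5.8) = 0.097.

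**Step 2: baseline against each response**
- cov(B, F−B) = 3.815 − 46.24 = −42.4.
- Correlation with change = −42.4/(6.8 × 8.5) = −0.73, so R² = 54%.
- Slope on change = −42.4/46.24 = −0.92 per point.
- R² for the follow-up score = 0.097² = about 1%.

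**Step 3: range over r.** With SDs 6.8 and 5.8, SD(change) = √(6.8² + 5.8² − 2r × 6.8 × 5.8) and corr(B, change) = (5.8r − 6.8)/SD(change).

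| Assumed r | SD of change | Corr. with change | R², change | R², follow-up score |
|---|---|---|---|---|
| 0 | 8.94 | −0.76 | 58% | 0% |
| 0.097 | 8.50 | −0.73 | 54% | 1% |
| 0.3 | 7.50 | −0.68 | 46% | 9% |
| 0.5 | 6.36 | −0.61 | 38% | 25% |
| 0.7 | 4.97 | −0.55 | 30% | 49% |

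For any r, the correlation with change cannot be smaller in size than √(1 − (5.8/6.8)²) = 0.52 (R² 27%). The contrast between the two responses does depend on r: it narrows as r rises and reverses at about 0.6, where the SD of change would be 5.71, well below 8.5.

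**Step 4: what the screen does to other factors.** Assume a factor correlates 0.3 with baseline IPSS and has no further link to outcome. Its correlation with change is 0.3 × −0.73 = −0.22, against 0.3 × 0.097 = 0.03 with the follow-up score. With 450 evaluable men (500 less the 10% of Section 8.3), t = −0.22 × √(448/(1 − 0.22²)) = −4.8, p < 0.001. At an assumed 0.2, p is about 0.002; at 0.1, about 0.12. The screen has no stated threshold. At the general two-sided 0.05 level of Section 8.5.1.3, unadjusted for multiplicity, the first two would pass.

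**Step 5: ranking by simulation.** 500 runs of 450 men, with baseline IPSS and ten other independent candidates, one truly correlated 0.3 with follow-up IPSS. With change as response, baseline IPSS ranked first in the univariate screen in every run, including at r = 0. With the follow-up score as response it ranked first in 0%, 0.2% and 51% of runs at r = 0, 0.097 and 0.3.

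**Step 6: the joint model.** If F = a + βB + γZ + e, then F − B = a + (β − 1)B + γZ + e. The coefficients γ of all other factors are identical and only the baseline coefficient moves, by −1. The simulation confirmed this to rounding error. The identity needs baseline IPSS to be in the model and unpenalised. Under LASSO as written, its coefficient may be shrunk or dropped, and correlated factors can then take up what is left.

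**The case against.** The strongest reply is that the response is not written as a change score. Where the plan means follow-up minus baseline it usually says so explicitly (Sections 8.2, 8.3, 8.5.2 and 8.5.3.6), while Section 8.5.3.1 uses similar over-time wording for a mixed-model trajectory. If the models describe IPSS levels over time, the subtraction coupling does not arise in this form. This stands, and it is why the point is conditional. The ambiguity itself still needs resolving, and the same edit resolves it.

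Baseline IPSS as a candidate is also inferred. The screen is said to cover every baseline characteristic, but clinical judgment could set this one aside. That is possible, though no rule requires it.

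A change model adjusted for baseline is equivalent to ANCOVA on the follow-up score for every other factor. This is correct for a joint model with unpenalised baseline, and it confines the harm to the unadjusted screen, the penalised baseline term and the reading of the baseline coefficient.

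The SDs come from an earlier cohort, which included 54 men with indwelling catheters at baseline, and are combined with a planning assumption. The implied r of 0.10 is therefore illustrative and not an estimate for this trial, so the range in the table should be read with it.

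Finally, the objective is exploratory and conditional on sufficient data, so the stakes are modest.

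**Conclusion.** The concern holds conditionally. If the response is change from baseline and baseline IPSS is a candidate, baseline IPSS will look like the strongest predictor largely through coupling, and the plan has no safeguard. On the document's figures it would account for 54% of change against about 1% of the 12-month score, with 46% against 9% and 38% against 25% at assumed correlations of 0.3 and 0.5. Factors correlated with baseline IPSS can be selected for that reason alone. The primary estimate is unaffected.

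A reader might infer three stronger conclusions that the documents do not support.

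- *The study will report severity as the dominant predictor, with high explained variation.* The plan contains no ranking rule and no commitment to report R².
- *The association is arithmetic alone.* The SD falls from 6.8 to 5.8, and the correlation of change with the average of the two scores, which reduces the coupling, is (33.64 − 46.24)/√(79.88² − 4 × 3.815²) = −0.16. A small real association is possible. Men who start higher may also truly have larger absolute reductions, even though a single arm cannot attribute these to PAE.
- *The Section 3.3 question would be answered wholly by an artefact.* The joint-model identity shows otherwise when baseline is included and unpenalised.

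**What to change.** In Sections 8.5.2.2 and 8.5.3.1:

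1. State the response as the follow-up IPSS: the 12-month score in 8.5.2.2, and the 3, 12 and 24 month scores for the over-time model in 8.5.3.1.
2. Include baseline IPSS as an unpenalised covariate in every screening model and every LASSO fit.
3. Report what the other factors add beyond baseline IPSS.
4. State that the slope of change on baseline will not be interpreted as evidence that more severe patients benefit more from PAE.

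The cost is SAP wording only. Baseline IPSS is already scheduled, and a change score needs it anyway, so no man who could contribute a change score is lost. Any explained-variation figure the sponsor chooses to report would probably be lower than under a change response.

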## 8.5.3 Analysis of the Secondary Endpoints

### 8.5.3.1 IPSS changes over time

The changes over time in the IPSS using the EAS will be modeled using a linear mixed model where country and patient will be considered a random effect. If there is evidence of non-linearity, a nonlinear mixed-effects model using a 3rd-degree

 Tibshirani, Robert (1996). "Regression Shrinkage and Selection via the lasso". Journal of the Royal Statistical Society. Series B (methodological). Wiley. 58 (1): 267–88. JSTOR 2346178.

polynomial will be implemented. The predicted curve and 95% confidence interval will be reported. Missing data will not be imputed.

Sensitivity analyses using complete cases and missing values replaced with an age-specific average will be performed.

A multivariate linear model will be developed to predict the IPSS changes over time. Univariate analysis will be performed analyses for all the baseline characteristics. Based on those results combined with clinical judgment, a final set of baseline characteristics will be created for use in the multivariate model. The LASSO regression analysis method will be used to perform variable selection and regularization.

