## 4 Study Design

This is a prospective, open label post market study to evaluate the long-term safety and effectiveness of PAE using Embosphere Microspheres. Up to 500 patients with LUTS due to BPH will be enrolled in this single arm post market study. All patients at sites who meet eligibility criteria will be offered participation. Long term effectiveness of PAE on LUTS will be evaluated by IPSS score at baseline, 3 months, 12 months, and 24 months. Note: All subjects will be asked to complete the IPSS. However, study subjects who have an indwelling bladder catheter will not be required to complete the IPSS; the IPSS questions may not be relevant to subjects with an indwelling bladder catheter. Safety will be assessed by evaluating device and procedure-related adverse events at the same time points, plus at 4 weeks following embolization. Erectile function will be assessed at baseline and 12 months by SHIM score. Additional treatments for refractory or recurrent LUTS due to BPH post prostatic artery embolization will also be recorded.

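### The IPSS-over-time model names no within-patient covariance; read plainly, it forces equal correlation on all visits and makes intervals for change from baseline too narrow

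*Combined protocol and SAP*

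**What the plan says.** Section 4 has effectiveness "evaluated by IPSS score at baseline, 3 months, 12 months, and 24 months". Section 8.5.3.1 analyses the course of IPSS in the evaluable set with a "linear mixed model where country and patient will be considered a random effect". It adds: "If there is evidence of non-linearity, a nonlinear mixed-effects model using a 3rd-degree" polynomial is to be used. On output it says "The predicted curve and 95% confidence interval will be reported", and on missing visits "Missing data will not be imputed". Complete-case and age-specific-mean analyses follow as sensitivity analyses.

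The section does not use the word intercept. It names no random slope, no residual or within-patient covariance structure and no robust standard error. It does not say whether the response is the IPSS itself or its change from baseline.

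The documents give SDs in two places. Section 1 reports 6.8 at baseline and 5.8 at both 1-3 and 9-16 months for the 286-patient cohort. Section 8.3 plans with "Standard Deviation = 8.5" for the 12-month change. They give no 24-month SD and no correlation between follow-up visits.

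**The concern.** A single random effect per patient, with independent residuals, produces compound symmetry: the same variance at every visit and the same correlation between every two visits. Baseline is measured before embolization and the other three scores after it, so equal correlation is doubtful on its face. The documents' SDs point the same way, because they imply almost no correlation across baseline. Scores from the same man after treatment would be expected to agree more closely than that.

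Two things are at stake. First, the model averages a low correlation with higher ones, so its standard error is too small for contrasts against baseline and too large for contrasts between follow-up visits. Second, this is the one IPSS analysis that leaves missing visits to the likelihood, and the likelihood predicts a missing score well only if the covariance is right. Under compound symmetry a missing 12-month score is predicted from baseline and the 3-month score with equal weight. Dropout related to early results is plausible here, since Section 7 ends data collection for men who go on to a non-PAE procedure for BPH.

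**Working it through.** The plan states no coverage or correlation for this model, so there is no figure of its own to reproduce. Coverage below does not depend on the sample size.

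**Inputs.** SD 6.8 at baseline and 5.8 at follow-up (Section 1); SD of change 8.5 (Section 8.3). Assumed: SD 5.8 at 24 months, the same baseline correlation at each follow-up visit, and a follow-up correlation r varied from 0.1 to 0.9.

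**Step 1, implied baseline correlation.** (6.8² + 5.8² − 8.5²) / (2 × 6.8 × 5.8) = (46.24 + 33.64 − 72.25) / 78.88 = 0.097. The covariance is 7.63 / 2 = 3.815.

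**Step 2, what compound symmetry fits.** With visit means unrestricted (a cubic through four visits is saturated), the fitted variance is the mean over visits and the fitted covariance is the mean over pairs.
- Mean variance = (46.24 + 3 × 33.64) / 4 = 36.79.
- Mean covariance = (3 × 3.815 + 3 × 33.64r) / 6 = 1.91 + 16.82r.
- Model SD of any change = √[2 × (36.79 − 1.91 − 16.82r)].

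**Step 3, coverage of the interval for change from baseline.** Coverage = 2Φ(1.96 × model SD / 8.5) − 1. The true SD of change between 12 and 24 months is √[2 × 33.64 × (1 − r)], which gives the last column.

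| r (assumed) | Model SD of change (true 8.5) | Baseline-contrast interval too narrow by | Coverage | 12-to-24-month interval too wide by |
|---|---|---|---|---|
| 0.1 | 8.15 | 4% | 94.0% | 5% |
| 0.4 | 7.50 | 12% | 91.6% | 18% |
| 0.6 | 7.04 | 17% | 89.6% | 36% |
| 0.8 | 6.55 | 23% | 86.9% | 78% |
| 0.9 | 6.28 | 26% | 85.3% | 142% |

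Simulation with a REML random-intercept fit (450 men, 2,000 runs per setting, complete data) gave 91.3-91.8% at r = 0.4 and 86.6-87.5% at r = 0.8. With 10% and 20% missing at 12 and 24 months it gave 91.6-92.8% and 87.7-88.6%.

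**Step 4, the interval the plan names.** For the predicted curve the model variance at each visit is 36.79 (country variance ignored).
- Baseline: √(36.79 / 46.24) = 0.892, so coverage is about 92%.
- Each follow-up: √(36.79 / 33.64) = 1.046, so coverage is about 96%.

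Neither depends on r.

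**Step 5, sensitivity to 8.5.** With a baseline correlation of 0.3 (SD of change 7.5), coverage over r = 0.4 to 0.8 is 93.1% to 87.7%.

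**Step 6, change from baseline as the response.** Each change has variance 72.25, and two changes have covariance 46.24 − 2 × 3.815 + 33.64r = 38.61 + 33.64r. The correlation is 0.72 at r = 0.4 and 0.91 at r = 0.8, equal for all pairs. A random intercept fits this exactly, and coverage is 95.0%.

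**Step 7, dropout (assumed mechanism).** In simulations with 13-16% dropout driven by the 3-month score and r of 0.5-0.7, compound symmetry overstated the 12-month improvement by roughly 0.1-0.3 points. An unstructured covariance left about 0.03 or less.

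**Step 8, a linear random slope.** Adding one does not repair the interval: coverage is about 86-92% over r = 0.4 to 0.8.

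**The case against.** The strongest reply is that Section 8.5.3.1 does not specify a wrong covariance; it leaves the covariance open. That is correct. Random intercepts with independent residuals are the plain reading of the sentence, not its wording. The reply does not remove the point, because an analyst following the text would fit that model, and nothing in the section directs otherwise.

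Second, the planned interval is for the predicted curve, and contrasts against baseline are not named. This also stands. The curve's interval is only mildly off. But the section concerns changes in IPSS, and Section 8.2 defines effectiveness as change from baseline, so readers will use the model for that contrast.

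Third, the response may be change from baseline, in which case little is wrong. A reader might infer from the cubic that baseline must be part of the response, since three follow-up visits alone cannot support a cubic. The documents do not settle this. The cubic is conditional on non-linearity, Table 1 allows IPSS at unscheduled visits, visit windows run to ±8 weeks, and Section 8.5.1.2 defines study day from actual dates. A cubic in study day without baseline is therefore possible, though weakly supported.

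Fourth, the effect is modest. With 450 men (500 less 10%) the correct half-width is 1.96 × 8.5 / √450 = 0.79 points. Narrowing it by 12-23% gives 0.69-0.60, against a fall of about 15 points in the 286-patient cohort (21.5 to 6.2). This stands as a limit on importance. The dropout bias is likewise below the ±1 target of Section 8.2 and rests on an assumed mechanism; the documents give only 10% missing.

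**Conclusion.** The concern holds in a qualified form. Read plainly, the model fits a covariance that conflicts with the documents' SDs, and its interval for change from baseline is too narrow whenever follow-up scores correlate with each other at least as strongly as with baseline. Intervals between follow-up visits are too wide.

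A reader might infer that coverage of 87-92% follows from the plan's SDs alone. It does not. Those SDs fix only the baseline correlation, and even that joins a cohort's SDs to a planning value with no stated link between them. The 87-92% needs an assumed follow-up correlation of 0.4-0.8 and an assumed 24-month SD of 5.8. Over correlations of 0.1 to 0.9 the range is 94.0% to 85.3%.

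Nor is the main result in doubt. The primary 12-month estimate in Section 8.5.2 has its own estimator and interval and does not use this model. Confidence is high for the direction and moderate for the size. The change should be made, because the sentence as it stands leads to wrong error bars and the repair is simple.

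**What to change.** In Section 8.5.3.1:
- State that the response is IPSS at the four scheduled visits, including baseline.
- Replace the patient random intercept with an unstructured within-patient covariance, with visit as a categorical factor, fitted by REML with Kenward-Roger degrees of freedom.
- Report the visit means and the 3-, 12- and 24-month contrasts against baseline, each with a 95% interval. The predicted curve may stay as a display.

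The covariance has 4 × 5 / 2 = 10 parameters. The evaluable set excludes men with a catheter at the end of the procedure. If that share matched the 54 of 286 catheterised at baseline in Section 1, 500 men would become about 405, or about 365 after 10% missing, which is still ample.

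The cost is a short SAP edit and no new data. The interval for change from baseline becomes somewhat wider, and unscheduled IPSS scores are not used in this model.
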